6.4 Methods

6.4.1 VO₂Max and determination of running speed

Participants will perform a two-stage graded exercise test on a treadmill to determine the speed of downhill running that elicits 70% VO_{2max}. For the first stage, VO_{2max} will be determined via a graded exercise test. The test will begin with participants completing a 4-min warmup at 4.8km/h, followed by 1 minute of passive rest. The graded exercise test will start between 8.0 and 9.6 km/h, with the velocity increasing by 1.6km/h every 2 mins until reaching a speed of 14.4km/h. At this point, incline will be increased by 2% every 2 mins until the participant reaches volitional exhaustion (Succi et al. 2022). Heart rate and rate of perceived exertion (RPE) will be recorded via heart rate monitor (Garmin HRM-Dual, Garmin, KS, USA) and RPE Scale (Borg, 1982), to confirm maximal effort. Expired air will be collected and the gas exchange will be analysed using the Metelyzer 3B (Cortex, Leipzig, Germany). The equipment will be calibrated prior to each test as per manufacturer's directions using standard gases.

The second stage of the treadmill test will be used to determine the running speed that elicits 70% VO_{2peak} at a decline of -6%. Participants will start running at the same speed as the first test. Speed will be increased by 1km every 2 mins for five stages. Regression analysis will then be performed to determine the speed that elicited 70% VO_{2max}. Participants will then rest for 30 minutes.

5.4.2 Familiarisation

Once running speed has been determined, the participants will then be familiarised with the downhill running protocol to be used in the experimental visits. This familiarisation visit will expose the participant to the eccentric strain and the subsequent muscle damage associated with downhill running (Southall-Edwards, et al. 2022). As muscle damage can have a detrimental effect on markers of bone formation (Huang, et al. 2022), the prior exposure of the running protocol to the participants should blunt the muscle damage response in subsequent bouts of downhill running due to the repeated bout effect (Khassetarash, et al. 2022).

6.4.3 Downhill running protocol

Participants will perform 45 min of treadmill running at 70% $VO_{2\max}$ at a -6% slope, one and half hours after a standardised breakfast (FED) or fasted (FAST). Downhill treadmill slope will increase Ground Reaction Forces (GRFs) relative to level walking (Gotschall and Kram, 2005).

6.4.4 Bone Mineral Density (BMD) measurement

Bone mineral density and whole body composition scans will be performed at the familiarisation visit with a dual-energy X-ray absorptiometry (DXA) scanner (Hologic). The lumbar spine (L1 through L4), femoral neck, trochanter, and total hip areas will be scanned for determination of areal BMD (g/cm²).

6.4.5 Bone turnover markers, cortisol, insulin and glucose measurements

Blood samples (around 10ml) will be collected into serum-separation tubes containing spray-coated silica and polymer gel for serum separation (BD Vacutainer venous serum separation tubes: Hemogard, Fisher Scientific, UK) for determination of bone turnover markers PINP and CTX-1. Measurements of bone turnover markers will be done at Bone Biochemistry Laboratory (The University of Sheffield, UK). Measurement of glucose, insulin, and cortisol will be done at the Chemical Chemistry laboratory (Sheffield Teaching Hospitals, UK).

6.4.6 Sample handling

Samples will be collected into Serum Separating Tubes (SST). Blood in SST tubes will be left to clot for 15-30 minutes at room temperature and centrifuged at 2000 g for 10 minutes. The serum will be aliquoted and stored at -80⁰C until analysis.

6.5 Setting for the project

Oversight of the study will be at Sheffield Hallam University. The study will be conducted at the Advanced Wellbeing Research Centre (Sheffield Hallam University, UK). The study will conform to all standards of Good Clinical Practice and will be overseen by an experienced academic.

The Principal Investigator is [name] (Senior Lecturer in Biomedical Science, Anglia Ruskin University School of Medicine) and co-investigators for the study are [name] (Senior Lecturer in Nutrition, Sheffield Hallam University), [name] (The University of Sheffield) and [name] (The University of Sheffield). [name] (Manchester Metropolitan University) will provide academic support for study concept and design. Data collection (after appropriate training) will be the responsibility of [name] registered at Anglia Ruskin University.

6.6 Participants

Participants will be healthy male adults aged 28 ± 4 years.

6.7 Recruitment

Participants will be invited to take part in the study by invitation email and by poster. Posters will be distributed around Sheffield Hallam City Campus Buildings. Invitation emails will be sent out to Food and Nutrition students studying on undergraduate and postgraduate Food and Nutrition courses within the Department of Service Sector Management.

Prospective participants will be followed up by telephone or email for screening to make sure that they meet the eligibility criteria for the study. Eligible participants will be sent an appointment letter to confirm their study visit.

6.7.1 Informed consent

All participants will give informed consent before enrolment on to the study. Each prospective participant will receive a participant information sheet giving details of the study and will have at least 24 hours to consider their participation in the study before attending their first study visit to give consent to participation. All participants will be given the opportunity to ask questions about the study before giving informed consent. Informed consent will be collected of each prospective participant by the principal investigator/co-investigator or another appropriately trained member of staff after training and

observation as assigned by the delegation log. Participants will also have the opportunity to ask any questions that they have during any of their study visits.

6.7.2 Inclusion/Exclusion criteria

Inclusion criteria will be:

- Male (females excluded to remove the interplay between menstrual cycle and bone turnover)
- Caucasian ethnicity
- Aged 28 ± 4 years
- Are physically active (meet the UK guidelines for physical activity of at least 150 minutes moderate intensity activity and/or at least 75 minutes of vigorous intensity activity per week)
- Otherwise, healthy, able and willing to participate and provide written informed consent

Exclusion criteria will include:

- Current smokers
- Excessive alcohol consumption (max 15 alcohol units/week)
- Any musculoskeletal injury/disabilities
- Any conditions known to affect bone metabolism (e.g. uncontrolled hyper-/hypothyroidism, hyperparathyroidism, hypo-/hypercalcaemia) or malabsorption syndromes (e.g. Crohn's disease, coeliac disease or inflammatory bowel disease).
- Taking any medication known to affect bone metabolism (such as glucocorticoids or bisphosphonates)
- Positive Covid-19 test within the last 8 weeks
- Suffered a fracture in the previous 12 months
- Sedentary status (see physical activity inclusion criteria above)
- Have been told by medical professionals that they should not take part in moderate to high intensity exercise
- Should not be a professional athlete or take part in significant competitive recreational activity (takes no more than 4 structured exercise sessions per week on average)
- History of diagnosed eating disorders

6.8 Outcome measures and participant involvement at each visit

All participants will be required to attend the Advanced Wellbeing Research Centre (AWRC) on four separate occasions.

At the **familiarisation visit** each participant will give informed consent. Consenting participants will complete a PAR-Q, undergo a $VO_{2\text{max}}$ test, and DXA scan to measure baseline bone mineral density and body composition. Baseline anthropometric measures, including height, weight, and BMI will be taken. Participants will be asked to follow a standardised diet three days prior to their second study visit. Participants will also be asked to refrain from strenuous physical activity during this period and will be asked to record their food and drink consumption in a diet diary.

At the **second visit**, each participant will arrive after a 12-hour overnight fast.

Counterbalancing measures will be used to assign participants to either the FASTED-exercised, FED-exercised or breakfast only conditions. During the FED-exercised or breakfast only arms, a standardised breakfast will be given at 8.30am. Exercise in the FED condition will take place 1.5 hours after breakfast has been administered (10.00am). When in the fasted condition, participants will also begin exercise at 10.00am.

Blood samples will be taken by cannulation for bone turnover marker measurement and hormone measurement at baseline (8.30am), pre-exercise (immediately before exercise), 15 minutes during exercise, 45 minutes (immediately post-exercise) and 2 hours post-exercise. Timings will also be consistent in the breakfast-only arm.

At the **third and fourth visits**, following crossover periods, participants will be assigned to the alternative conditions and study measurements repeated as per second visit.

6.8.1 Summary of participant involvement by study time point

Study Time Point	Familiarisation Visit	First Pre-trial stage (3 days before visit 2)	Visit 2	Second Pre- trial stage (3 days before visit 3)	Visit 3	Third Pre-trial stage (3 days before visit 3)	Visit 4
Activity							
Informed Consent	X						
Demographic data	X						
Anthropometry (Height, weight & BMI)	X						
PAR-Q	X						
DXA Scan (Hip, Spine and Body composition)	X						
VO2Max Measurement	X						
Downhill Running Familiarisation	X						
Diet Diary		X		X		X	
Refrain from vigorous physical activity		X		X		X	
Follow standardised dietary advice		X		X		X	
Breakfast only (no exercise) or FED- exercised or FASTED- exercised condition			X		X		X
Blood samples for biochemical measurements			X		X		X
Urine Samples			X		X		X
Participant expenses given (£100 gift voucher)							X

6.8.2 Summary of biochemical measurements by study visit time point (for both fasted and fed conditions)

Study Visit Time Point	Baseline (8.30am)	Immediately Pre-exercise (10.30am)	During Exercise (15-minutes)	Immediately Post-Exercise Completion (45-minutes)	2-hours Post-exercise
Biochemical measurement					
CTX	X	X	X	X	X
PINP	X	X	X	X	X
Glucose	X	X	X	X	X
Insulin	X	X	X	X	X
Cortisol	X	X	X	X	X

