6.3 Study measurements

The blood samples will be collected (10ml) by cannula at baseline, immediately pre-exercise, and after 15 minutes and 45 minutes of exercise and after 2-hours of recovery. The osteogenic response to exercise will be determined by measuring a marker of bone formation; P1NP and a marker of resorption; CTX-1.

To assist in making inferences on the possible hormonal interactions with mechanical, cardiovascular, and psychological stress in our study, and thus their contribution to changes in bone markers, we will also measure plasma concentrations of cortisol; a marker of physiological and psychological stress and because of its promotion of bone resorption. Insulin and glucose measurements will allow us to assess the change of concentrations in fasted and fed states. Urine samples will be collected at baseline, immediately before and after the exercise. Samples will be frozen at -80°C and analysed for bone turnover biomarkers later with the permission of participants.

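### Table 6.8.2 times the pre-exercise blood sample at 10.30am, 30 minutes after the stated 10.00am exercise start: correct the cell and give the breakfast-only arm its own clock times

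*Combined protocol and SAP*

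**What the plan says.** Section 6.8 sets the timetable in words. On breakfast: "During the FED-exercised or breakfast only arms, a standardised breakfast will be given at 8.30am". On the fed exercise arm: "Exercise in the FED condition will take place 1.5 hours after breakfast has been administered (10.00am". On the fasted arm: "When in the fasted condition, participants will also begin exercise at 10.00am". It defines the second blood sample as "pre-exercise (immediately before exercise" and says of the non-exercise control: "Timings will also be consistent in the breakfast-only arm".

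Sections 6.1 and 6.4.3 each give the same 90-minute gap between meal and run. Section 6.4.3 sets the run at 45 minutes. Section 6.3 lists the samples after baseline in the order "immediately pre-exercise, and after 15 minutes and 45 minutes of exercise and after 2-hours of recovery".

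The table in section 6.8.2 prints only two clock times: 8.30am for baseline, and the column headed "Immediately Pre-exercise (10.30am". Its title says it applies "for both fasted and fed conditions". The breakfast-only condition is not named there, although table 6.8.1 schedules blood samples at all three condition visits.

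**The concern.** The only clock time printed against the pre-exercise sample itself is 10.30am, and this cannot be reconciled with the rest of the protocol. With a 10.00am start, the sample would be drawn during the run.

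The exposed arm is breakfast-only. It has no run to anchor the pre-exercise, 15-minute, 45-minute or 2-hour labels, so staff must work from a clock. The right times can be derived from section 6.8, but the one printed against this draw is wrong. If staff used it, the control samples would be taken later after the meal than the FED-exercised samples carrying the same labels.

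Section 6.9 pools the three groups by time point when there is a time effect without an interaction, and compares the groups at every time point when the condition-by-time interaction is significant. A 30-minute offset would then mix time since the meal with the effect of exercise in the comparison with the control. Section 5.1 itself describes CTX as falling within an hour of feeding and being down by about half after 2 to 3 hours, so time since the meal is relevant to this marker.

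**Working it through.** **Inputs.** Breakfast at 8.30am and exercise at 10.00am (6.8); 90 minutes from meal to run (6.1, 6.4.3, 6.8); 45-minute run (6.4.3); samples just before the run, at 15 and 45 minutes, and 2 hours after it ends (6.3, 6.8); printed pre-exercise time 10.30am (table 6.8.2).

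**Step 1: try to reproduce the printed time.** 8.30am + 90 min = 10.00am. The printed 10.30am is not reproduced.

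**Step 2: test 10.30am against a 10.00am start.** 10.30 − 10.00 = 30 min, which lies inside the 45-minute run. The 15-minute sample is due at 10.15am, so a 10.30am draw would follow it by 15 min. Sections 6.3 and 6.8 put the two in the opposite order.

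**Step 3: test 10.30am as the true start.** 10.30 − 8.30 = 120 min from meal to run, against 90 in three sections. The cell is the outlier.

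**Step 4: set out the schedules.** The 2-hour sample falls at start + 45 + 120 = start + 165 min.

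| Sample | Counted from 10.00am | Min after breakfast | Counted from 10.30am | Min after breakfast |
|---|---|---|---|---|
| Pre-exercise | 10.00am | 90 | 10.30am | 120 |
| 15 min | 10.15am | 105 | 10.45am | 135 |
| 45 min | 10.45am | 135 | 11.15am | 165 |
| 2 h post-exercise | 12.45pm | 255 | 1.15pm | 285 |

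**Step 5: consequences in the breakfast-only arm.**

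- All four draws counted from the cell: each is 30 min late, and the interval from the pre-exercise to the 2-hour sample is 285 − 120 = 165 min, the same as the correct 255 − 90 = 165 min. The interval is kept; its position after the meal moves.
- Only the pre-exercise draw taken from the cell, with the rest on the 10.00am clock: the interval shrinks to 255 − 120 = 135 min, and the draw comes after the 15-minute sample. Staff would probably notice that order.

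These are timing figures only. The documents give no basis for turning a 30-minute shift into a CTX difference, and none is claimed.

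**The case against.** The strongest reply is that the protocol already answers the question. Section 6.8 gives the meal time, the start in both exercise arms, the relative definition of the sample and the rule that the breakfast-only arm keeps the same timings. The column label itself says the draw precedes exercise. On this view it is a one-cell slip with one workable reading, and harm requires staff to follow the table against the text. This stands, and it is why the point is minor. It does not justify leaving a wrong time in the sampling table.

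A second reply is that the table title may not cover the breakfast-only arm, in which case 10.30am does not govern there. Alternatively, fed may loosely include that arm, in which case the title is adequate. The protocol generally uses FED for the exercised arm and names breakfast-only separately, so the title does not settle it. Naming all three conditions would help, but it is clarification only. The study-specific SOPs listed in Appendix A may also carry the correct times; they are not available, so they neither confirm nor remove the risk.

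A third reply concerns the remedy. Fixed clock times in every arm would conflict with the run-relative definitions whenever a run starts late. This is right, and the fix below allows for it.

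A reader might go further and infer that the baseline of the primary endpoint is compromised. The documents do not support that. The primary outcome in section 6.2 compares the fasted-exercised and fed-exercised arms, and in both the draw is tied to the start of the run.

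**Conclusion.** The point holds as a minor inconsistency in the sampling schedule. The table entry is 30 minutes late; 10.00am is the only time consistent with sections 6.1, 6.4.3 and 6.8. The comparison at risk is the one with the breakfast-only control, where samples could fall 30 minutes later after the meal than their FED-exercised counterparts. That outcome assumes that staff take the time from the table rather than from section 6.8 and count the later draws from it. No effect on the primary fasted versus fed comparison is shown. The discrepancy is not evidence of an intended 120-minute gap between meal and run, and it raises no question about the design itself.

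**What to change.** - In table 6.8.2, change the pre-exercise time from 10.30am to 10.00am.
- In the two exercise arms, keep the run-relative definitions as governing and mark any clock times as nominal, so that a late start creates no new conflict.
- For the breakfast-only arm, state 8.30am, 10.00am, 10.15am, 10.45am and 12.45pm, that is 0, 90, 105, 135 and 255 minutes after breakfast. Its samples then match the FED-exercised arm in time since the meal.
- Optionally, name the fasted-exercised, fed-exercised and breakfast-only conditions in the table title.

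The cost is one cell and a line of clock times, plus the title if wanted, in a minor amendment. No visits, samples or participants are added and the intervention does not change.

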6.9 Statistical analysis

Normality will be assumed if Shapiro-Wilk test is not statistically significant ($P > 0.05$). Where data is normally distributed, the data will be presented as mean and standard deviation (SD). Where data were not normally distributed, data will be presented as median and IQR.

Biochemical data will be analysed using a linear, mixed model (LMM), with factors 'condition' and 'time point' as fixed effects and 'participants' as a random, within-group effect. The assumptions of the LMM (homogeneity of variance and normality) will be investigated by examining the distribution of residuals and the pattern of residuals versus fitted values. Where non-normality or non-constant variance are observed, a log transformation will be applied to the data so that the assumptions are satisfied.

Where there is a significant main effect of *Time* but no significant *Condition* x *Time* interaction, each subsequent time point will be compared against 'Baseline' using a pooled mean from the three groups using Dunnett's test. If the *Condition* x *Time* interaction is significant, within each group, each time point will be compared against baseline using a Dunnett's test and groups will be compared to each other at all time points using the Student Newman-Keuls (SNK) test.

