6.2 Power calculation

The primary outcome of this study is the difference in change in CTX concentration between the pre-exercise and 2-hour post-exercise timepoints between the fasted-exercised and fed-exercised arms.

Based on changes in CTX from a previous study (Scott et al., 2012), we designated 30% as a minimally significant difference and that 30% would be approximately 0.168 µg/l. We calculated a standard deviation of 0.2 µg/l based on results from our previous studies with serial measurements of CTX. To achieve 80% power for demonstrating this mean difference as statistically significant at the 2.5% two-sided level requires a total of 16 participants (including 2 additional participants for withdrawals). This sample size is in line with that of other studies in this area.

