that they should not take part in moderate to high intensity exercise will be excluded). Appropriate risk assessments will be carried out with risk mitigating controls put in place.

Participant samples will be stored at the AWRC before being transferred to the -80°C freezer on the 12th Floor of the [name] (Food and Nutrition Subject Group) at the end of data collection. Samples will be stored here until the completion of the study. Other data will be stored securely in accordance with the Data Protection Act 2018 and potentially used for future research (with the consent of participants).

Participants will be informed of their right to withdraw from study at any point.

Section 10: Methods for disseminating research results

It is intended that the results of this study will be published in a peer-reviewed journal as well as presented at national and/or international conferences. The data will be used as preliminary data for external grant application.

Section 11: Strategy for taking the work forward

This study is a pilot study and data collected will be used to form part of a wider programme of the study of the synergistic effects of feeding interventions on the response of skeleton to physical activity in young and elderly humans including females and the concurrent role of candidate osteotropic hormones in bone homeostasis.

Section 12: Costing the project

The project will be funded through Anglia Ruskin University Higher Education Quality-related Research (QR) funding, local SHU fieldwork funding and PhD funding, according to the breakdown below:

Expense	Amount per unit (£)	Total Cost (£)	Comments
Office consumables		£350.00	QR funding
Clinical consumables		£2,500.00	QR funding
Participant breakfast		£300.00	QR Funding
Technical training (e.g. Cannulation training)		£700.00	SHU Fieldwork funding
[name]		£0.00	Work planned time

[name]		£0.00	Work planned time + SRfR time
Participant Inconvenience Payments	£100	£1,600.00 (16 x £100.00)	SHU Fieldwork Funding
Biomarker analysis (80 measurements x 3)		£5,000.00	Covered by QR funding
Hormone analysis (insulin and cortisol - (100 measurements x 2 each cross-over study))		£6,850.00	Covered by QR funding
Total		£17,300.00	

Section 13: Funding

The project is funded through ARU Higher Education Quality-related Research (QR) funding, and by internal SHU Fieldwork Funding.

Section 14: References

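### Section 6.9 picks mean or median by a Shapiro-Wilk test on 14 to 16 men, unlinked to the model's scale, and plans no estimate or interval for the primary CTX contrast

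*Combined protocol and SAP*

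**What the plan says.** Section 6.9 opens with a rule for presentation: "Normality will be assumed if Shapiro-Wilk test is not statistically significant", with P > 0.05 as the criterion. Data that pass are shown as mean (SD). For the rest, "Where data were not normally distributed, data will be presented as median and IQR". The section does not say whether the test is applied to each condition-by-time cell, to each analyte as a whole, or to something else.

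Inference follows a separate route: "Biochemical data will be analysed using a linear, mixed model (LMM), with factors 'condition' and 'time point' as fixed effects", with participant as a random effect. The model's assumptions "will be investigated by examining the distribution of residuals and the pattern of residuals versus fitted values", and the remedy for a failure is a log transformation.

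If the Condition x Time interaction is significant, each time point is compared with baseline within each condition by Dunnett's test, and "groups will be compared to each other at all time points using the Student Newman-Keuls (SNK) test". If only Time is significant, the three conditions are pooled and compared with baseline.

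Section 6.2 defines the primary outcome as the difference, between the fasted-exercised and fed-exercised arms, in CTX change from pre-exercise to 2 hours post-exercise. It adds that "we designated 30% as a minimally significant difference", taken as about 0.168 µg/l. On use of the results, Section 10 says: "The data will be used as preliminary data for external grant application".

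**The concern.** There are two linked weaknesses in how results will reach the reader.

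First, a non-significant Shapiro-Wilk test at this sample size does not establish normality, so the choice of summary depends partly on chance. It is also made independently of the model's residual check. An untransformed model compares arithmetic means, and a logged model compares geometric means. Nothing in Section 6.9 ensures that the displayed summaries are on the same scale. On a cell-by-cell reading, the same marker could be shown as a mean under FAST and a median under FED at the same time point.

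Second, the planned comparisons do not produce the quantity that Section 6.2 calls primary. SNK is a stepwise procedure that gives significance decisions without confidence intervals. It is applied at single time points rather than to changes, and only after a significant interaction. Reading the result against the trial's own 30% threshold, or carrying it into a grant application, requires an estimated difference in change with its uncertainty.

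**Working it through.** **Inputs.** Section 6.2 gives 16 participants including 2 for withdrawals (so 14 to 16), SD 0.2 µg/l, difference 0.168 µg/l = 30%, 2.5% two-sided level and 80% power. Section 6.1 gives three conditions. Section 6.8 gives five blood samples per visit. Each analyte therefore has 3 x 5 = 15 cells.

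**Step 1: the plan's own figure.** A paired normal approximation gives n = (SD x (z for 0.9875 + z for 0.80) / difference)² = (0.2 x (2.241 + 0.842) / 0.168)² = 13.47. This rounds up to 14, plus 2 = 16, so the figure is reproduced. Here 0.2 acts as the SD of a paired difference.

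**Step 2: assumed spread of CTX levels.** 0.168 / 0.30 = 0.56 µg/l, and 0.2 / 0.56 = 0.36. Reading 0.36 as the CV of levels between men is an assumption, and Step 1 shows that it is not the only reading.

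**Step 3: cell-by-cell reading, independent normal cells.** The chance of at least one failure in 15 cells is 1 - 0.95^15 = 53.7%.

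**Step 4: simulation with correlated cells.** Shapiro-Wilk was run at 0.05 in each of 15 cells, with n = 14 and 16. A table is mixed if at least one cell, but not all 15, is flagged. Where two correlations are shown, they are within visit / between visits.

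| Data | Correlation | Cells flagged | Table mixed |
|---|---|---|---|
| Exactly normal | 0.5 | about 5% | 51-52% |
| Exactly normal | 0.8 | about 5% | 40-42% |
| Exactly normal | 0.9 | about 5% | 31-32% |
| Exactly normal | 0.95 | about 5% | 22% |
| Log-normal, CV 0.36 | 0.8 / 0.6 | 21-24% | 85-89% |
| Log-normal, CV 0.36 | 0.9 / 0.7 to 0.8 | 21-24% | 70-80% |
| Log-normal, CV 0.36 | 0.95 / 0.9 | 21-24% | 55-57% |
| Log-normal, CV 0.3 | 0.95 | 17-19% | 41-43% |
| Log-normal, CV 0.6 | 0.8 / 0.6 to 0.95 / 0.9 | 42-49% | 71-97% |

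At CV 0.36 every cell is skewed, yet the test misses about three quarters of them. A pass is therefore weak evidence of normality.

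**Step 5: one test per analyte.** Mixing within an analyte is then 0% by construction. However, such a test pools repeated values from conditions and times with different means, so it does not test normality within a cell. The resulting choice is still unconnected to the model's scale.

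**Step 6: planned comparisons against the primary contrast.** The primary contrast is (FAST at 2 h - FAST pre-exercise) - (FED at 2 h - FED pre-exercise).
- Dunnett comparisons within a condition start from baseline, which Section 6.8 places at 8.30 am, not from the pre-exercise sample, and they do not compare conditions.
- SNK compares conditions, but at one time point at a time.
- Without a significant interaction, Section 6.9 plans no FAST-versus-FED comparison at all.

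No planned output is the primary contrast, and none is specified with an interval.

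**The case against.** The strongest reply is that the Shapiro-Wilk rule concerns presentation only. The mixed model does not use its result, so no test or decision changes. That is correct.

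The mixing argument also needs a cell-by-cell reading that Section 6.9 does not state. The rule might be meant for one test per analyte, or for the baseline characteristics that Section 6.1 collects to describe the sample. That stands too, and is why the probabilities are conditional.

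Several stronger readings are tempting but unsupported:
- A reader might infer that CTX tables will probably mix summaries. This fails for exactly normal data with strong correlation (22-42% at 0.8 to 0.95), and at CV 0.3 with correlation 0.95 (41-43%).
- A reader might infer that the summaries cannot match the model. They can: mean (SD) matches an untransformed model, and for log-normal data the median approximates the geometric mean of a logged one. Only a mixed table must mismatch somewhere.
- A reader might set the mean-median gap against 0.168 µg/l. In flagged cells the simulated gap is 10-11%, about 0.06 µg/l at 0.56 µg/l, but those cells are selected for looking non-normal. The population gap at CV 0.36 is 1 - 1/√(1 + 0.36²) = 5.9%, or 0.059 x 0.56 = 0.033 µg/l. Either figure is a gap in one cell's level and does not bias a contrast defined on change.
- A reader might say that Dunnett's method offers no interval. It has standard simultaneous intervals; Section 6.9 simply does not ask for them.

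Finally, a fitted mixed model yields estimates and standard errors, and silence is not exclusion. True, but the section does name its between-condition comparison, and that one gives no interval and depends on the interaction test. The primary contrast should not depend on what is added at reporting.

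**Conclusion.** The point holds as a reporting and interpretation weakness that should be corrected. Type I error and power are unaffected by the Shapiro-Wilk rule.

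The weakness of the rule and its lack of a link to the model follow from the text and from n = 14 to 16. The size of the mixing problem is less certain. The 55-89% figure rests on the cell-by-cell reading, log-normal data, a CV of 0.36 and the assumed correlations. The range is 22-52% if the data are exactly normal, and zero under one test per analyte.

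The missing estimate and interval for the primary contrast rests on no simulation. It follows from setting Section 6.9 beside Section 6.2, and is the weightier half of the point.

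**What to change.** In Section 6.9:

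1. Delete the Shapiro-Wilk rule. Use one summary per analyte in all 15 cells, on the scale of that analyte's model: mean and SD if modelled raw, geometric mean with geometric SD or CV if logged. Plot the individual values.
2. Whatever the interaction test shows, report from the mixed model (with its Condition x Time term) the FAST-minus-FED difference in CTX change from pre-exercise to 2 hours post-exercise, with a confidence interval. Use 97.5% to match the 2.5% two-sided level in Section 6.2, with 95% alongside if wanted. Read it against 0.168 µg/l. If CTX is logged, report it as a ratio and read it against 30%, stating beforehand how 30% is expressed as a ratio.

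The cost is a few sentences, with no new data and no change to trial conduct. The one downside is that a few skewed cells will be shown as means, which the plot of individual values covers.
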